## **A prospective longitudinal cohort study to determine the incidence of HIV-associated non-AIDS conditions in newly diagnosed HIV-infected individuals initiating integrase inhibitor-based and other anti-retroviral regimens**

### **Background**

Integrase strand transfer inhibitor (INSTI) based-therapy is currently the recommended antiretroviral regimen in most guidelines. Efficacy in terms of virological suppression of INSTI-based regimens was either superior or non-inferior to other comparators in clinical trials performed in both treatment naïve and experienced individuals. Moreover, unlike other classes of anti-retroviral agents, transmitted drug resistance was uncommon even after years of introduction of INSTI on a population level, potentially allowing this class of drug to remain as recommended first-line treatment in the future.

Previous clinical trials comparing INSTIs and other anti-retroviral regimens in treatment-naïve individuals consistently showed lower discontinuation rates secondary to adverse reactions. For treatment-experienced individuals, switching from non-nucleotide reverse transcriptase inhibitor (NNRTI) or protease inhibitor (PI)-containing to an INSTI-containing regimen often resulted in better lipid profiles as well as tolerability and patient satisfaction. INSTIs have been shown to improve blood pressure control in those with underlying hypertension receiving anti-hypertensive treatment. INSTI also had lesser decline in bone loss when compared to protease inhibitors. On the other hand, integrase inhibitors have been reported to be the cause of metabolic complications, and neuropsychiatric adverse reactions. Transient drop in renal function and other renal complications in individuals taking some INSTIs had also been reported.

Currently, with the availability of very effective anti-retroviral agents as well as aging of the HIV-infected population, management of HIV-infected individuals should also include the assessment, prevention and management of multiple HIV-associated non-AIDS conditions (HANA) that are known to be more prevalent in HIV-infected individuals. In Asia, many of these conditions, like diabetes, dyslipidemia, lipodystrophy, osteopenia and osteoporosis, chronic kidney disease, and fatty liver disease and liver fibrosis, and retinal diseases were prevalent in HIV-infected individuals. Most of these studies, however, were performed in individuals taking older anti-retroviral agents. Whether the increase of INSTI use in the region is associated with lower incidence of development of HANA is currently unknown. Moreover, clinical trials of anti-retroviral therapy seldom included older individuals with multiple co-morbid illnesses. Currently available real world data on clinical use of INSTI seldom included HANA in their evaluation. Longitudinal real world data in Asia evaluating the incidence of various HANA after initiation of different anti-retroviral regimens are also limited, despite these conditions cause significant burden of disease in the Asian population.

The understanding of incidence of various HANA conditions in relation to the class of anti-retroviral drugs used will potentially aid to improve outcomes in the aging HIV-infected population by optimizing their anti-retroviral regimen. As data on HANA in the Asian/Chinese HIV-infected population is currently lacking, results of studies performed in Hong Kong which mainly comprises of predominantly Chinese and other Southeast/South Asian HIV-infected

individuals, would likely benefit other HIV-infected populations in China, Taiwan and other surrounding Asian countries.

This study, therefore, aims to evaluate the incidence of various HANA conditions in a cohort of newly diagnosed HIV-infected individuals in Hong Kong initiating anti-retroviral treatment. The incidence of various HANA conditions will be evaluated for those receiving INSTI versus other non-INSTI-based regimens.

### **Objectives**

- To determine the incidence of HANA conditions in newly diagnosed HIV-infected individuals initiating integrase inhibitor-based and other anti-retroviral regimens in an Asian population
- To evaluate the risk factors associated with developing each HANA condition
- To set up an electronic platform for systematic collection of clinical data and establishment of a clinical decision tool for clinical risk prediction and improvement in clinical management

### **Clinical hypotheses**

Individuals initiating integrase inhibitor-based anti-retroviral regimens will develop lower incidence of HANA.

### **Study design**

This is a prospective, longitudinal, cohort study. 400 newly diagnosed HIV-infected individuals attending HIV clinics in Hong Kong will be recruited. Clinical assessment, and laboratory and imaging studies will be performed at baseline prior to initiation of anti-retroviral regimen, than annually thereafter for 5 years. Choice of anti-retroviral regimen will be decided by the in-charge HIV physician. Incidence of development of various HANA conditions will be determined for those initiated INSTI-based regimens and other anti-retroviral regimens. An electronic platform will be used to formulate risk prediction for various clinical outcomes, and serve as a clinical decision support tool.

### **Subjects and sampling**

#### **a. Study population**

All newly diagnosed HIV-infected individuals naïve to ART meeting inclusion criteria, who attend the government HIV clinic, which is the largest HIV clinic in Hong Kong, will be invited to participate in this study. Subjects will also be referred by non-governmental organizations providing support to HIV-infected individuals at the time of diagnosis.

#### **b. Inclusion criteria:**

1. Confirmed HIV infection by HIV antibody or RNA test
2. Age  $\geq 18$  years old
3. Anti-retroviral treatment naïve, within 6 months of initiation of anti-retroviral drugs, or switching ART regimens within 24 months
4. Agree to initiate anti-retroviral therapy (ART) as determined by in-charge HIV physician

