## **Data collection and investigations**

- a. Eligible subjects will attend Infectious Diseases clinic at the Prince of Wales Hospital for assessment.

The first study visit will be scheduled before or within four weeks of initiation of ART. Annual visits will be scheduled thereafter for 5 years. During each study visit, demographic and clinical data will be collected. Physical examination will be performed. Blood and urine tests will be done at fasting state. Imaging, including ultrasonography of carotid arteries, DEXA scan and fibroscan, will be performed. Stool samples will be collected for microbiota study.

- b. Clinical data

A structured standardized research tool will be used to collect demographic and clinical data:

1. Age, gender, smoking status, alcohol consumption, exercise
2. Co-morbid illnesses, including history or new diagnoses of hepatitis B and C, diabetes, dyslipidemia, hypertension, metabolic syndrome, and cardiovascular diseases, as well as all comorbidities included in the Charlson comorbidity score
3. Date of HIV diagnosis, latest CD4 counts, latest HIV viral load
4. Medication history, including anti-retroviral drugs and other medications

- c. Physical examination and anthropometric measurements

1. Body weight and height, and body mass index
2. Hip and waist circumferences
3. Blood pressure
4. For subjects aged  $\geq 50$  years old, assessment of frailty, including hand grip strength, balance tests, 6-metre walking speed, will be performed
5. Neurocognitive assessment
  - i. International HIV dementia scale  
<https://www.hiv.uw.edu/page/mental-health-screening/ihds>
  - ii. Montreal Cognitive Assessment
  - iii. Symbol digit modality test (SDMT)
  - iv. Action fluency: ask the patient to say as many things that people do in 1 minute
  - v. Cogstate platform neurocognitive tests
  - vi. DASS 21 for screening of mood
  - vii. Lawton Instrumental Activities of Daily Living
6. Quality of life assessment
  - i. EQ-5D-5L questionnaire
7. Lung function test
  - i. FEV1 and FVC will be performed in smokers.

- d. Blood tests:

The following blood tests will be performed after an 8-hour fast:

1. Glucose, insulin, HbA1c
2. Total cholesterol, LDL cholesterol, HDL cholesterol, triglyceride, apolipoprotein A and apolipoprotein E
3. Complete blood count, creatinine, urate, calcium, phosphate, urea, ferritin

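### Inclusion criterion 3 admits people already on ART, against the newly diagnosed, ART-naive cohort and the baseline windows stated elsewhere, and the analysis pools all entry routes

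*Combined protocol and SAP*

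**What the plan says.** All references are to the combined protocol and SAP.

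- **Objectives and Clinical hypotheses.** The first objective concerns the "incidence of HANA conditions in newly diagnosed HIV-infected individuals initiating integrase inhibitor-based" and other regimens. The hypothesis is that "Individuals initiating integrase inhibitor-based anti-retroviral regimens will develop lower incidence of HANA".
- **Study design.** 400 newly diagnosed people are to be recruited. Assessments "will be performed at baseline prior to initiation of anti-retroviral regimen", then yearly for 5 years.
- **Study population.** The invitation goes to "All newly diagnosed HIV-infected individuals" who are naive to ART and meet the inclusion criteria.
- **Inclusion criteria.** Item 3 accepts treatment-naive people and also those "within 6 months of initiation of anti-retroviral drugs, or switching ART regimens within 24 months". Item 4 reads "Agree to initiate anti-retroviral therapy (ART) as determined by in-charge HIV physician". Being newly diagnosed is not an item in the list.
- **Data collection and investigations.** "The first study visit will be scheduled before or within four weeks of initiation of ART". "Annual visits will be scheduled thereafter for 5 years". Date of HIV diagnosis and antiretroviral drug history are among the data collected.
- **Sample size calculation.** The planning risk is 20% for metabolic syndrome at 96 weeks, counted from the start of ART. With 400 people the interval is given as 16% to 24%. A second statement covers an odds ratio of 2 with a lower bound of 1.0 after allowance for multiple risk factors.
- **Statistical analysis.** Item b gives incidence by class of regimen started. Item c analyses the whole cohort, names subgroups by regimen class only, and allows treatment-related variables in the models.

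**The concern.** The objective and the hypothesis are about what happens after people start ART. Criterion 3 lets in people whose first ART start lies before study entry, and nothing in the analysis separates them.

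For such people the study baseline is not a pre-treatment baseline. A condition that arose on earlier ART is already present at the first visit and so counts as prevalent, not incident. Baseline covariates are measured after treatment has begun. Person-time runs from the study visit, which is not the start of ART.

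The physician chooses the regimen, so treatment stage and prior regimen may differ between the INSTI and non-INSTI groups. A crude or incompletely adjusted class comparison could then reflect those differences.

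**Working it through.** **Step 1. Set each entry route against the sections.**

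| Entrant | Criterion 3 | ART-naive at entry (Study population) | Baseline before ART (Study design) | First visit before or up to 4 weeks after ART start (Data collection) |
|---|---|---|---|---|
| Treatment-naive | admitted | yes | yes | yes |
| Up to 4 weeks on ART | admitted | no | no | yes |
| 4 weeks to 6 months on ART | admitted | no | no | no |
| Regimen switcher | admitted | no | not for first ART | not for first ART, unless the switch falls in the first 4 weeks |

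The second row is a small mismatch: someone invited while naive and seen within four weeks of starting satisfies both the Study population and the first-visit wording. The third and fourth rows are the real conflict. Criterion 4 also fits poorly with people already on treatment.

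The 24-month limit has no stated reference point. It could mean a switch made in the past 24 months, a switch expected in the next 24, or a switch made within 24 months of first ART. Under the first of these, time since first ART has no upper limit.

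**Step 2. Does the analysis separate the routes?** It does not. Grouping is by regimen started, and a switcher also starts a regimen, so that word does not create a starter set. No rule is given by entry route.

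The clocks also differ. For someone entering at 6 months (about 26 weeks), the two-year visit at 104 weeks after baseline falls at 104 + 26 = 130 weeks on ART. The planning risk is stated at 96 weeks from ART start.

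**Step 3. Reproduce the plan's interval.** Inputs from the Sample size calculation: p = 0.20, n = 400. Formula: p ± 1.96 × √(p(1 − p)/n).

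- 1.96 × √(0.16/400) = 0.0392, giving 16.1% to 23.9%. This matches the stated 16% to 24%, so the figure itself is sound.

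**Step 4. The same interval for starters only.** The documents give no number of starters, so the values below 400 are assumptions.

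| Starters | Half-width (points) | 95% interval |
|---|---|---|
| 400 | 3.9 | 16.1% to 23.9% |
| 360 | 4.1 | 15.9% to 24.1% |
| 280 | 4.7 | 15.3% to 24.7% |
| 200 | 5.5 | 14.5% to 25.5% |

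A half-width of exactly 4 points needs 1.96² × 0.16 / 0.04² = 384.2, so 385 starters.

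**Step 5. The odds-ratio statement.** Lower bound = 2 × exp(−z × SE), with SE = √(sum of 1/expected cell counts). An even exposure split is assumed throughout.

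- If 20% is the unexposed risk, the exposed risk is 33.3%. At n = 400, SE = √(1/66.7 + 1/133.3 + 1/40 + 1/160) = 0.2318. With z = 1.96 the bound is 1.27.
- At n = 280, SE = 0.2318 × √(400/280) = 0.2771. Bonferroni for four factors (z = 2.498) gives 1.001; for five factors (z = 2.576) it gives 0.98.
- If 20% is the overall risk, the two risks are 14.57% and 25.43%, and SE = 0.2580 at n = 400. Five factors give 1.03. If only 80% are evaluable (assumed, n = 320), SE = 0.2885 and the bound is 0.95, with no pre-treated entrants at all.

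Whether the bound stays above 1.0 therefore turns on the number of factors, the reading of 20% and evaluability, as well as on entry route.

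**The case against.** The strongest reply is that the document, read as a whole, describes a starter cohort and criterion 3 is the outlier. The Study population wording requires people to be naive and also to meet the criteria, community organisations refer people at diagnosis, and criterion 4 speaks of initiating ART. On that reading few or no pre-treated people enter. This is a fair account of the likely intent. It does not remove the conflict, because eligibility is applied from the list of criteria and the list says otherwise.

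It can also be said that initiation may mean starting the new regimen. That works for the hypothesis and the baseline sentence taken alone, but not for the newly diagnosed, ART-naive wording elsewhere.

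A third reply is that diagnosis date and antiretroviral history are collected and treatment-related variables may enter the models. This stands in part. A reader might infer that nobody could ever tell whom the incidence figures describe; that goes too far, since the entry mix could probably be reported and adjusted for. What is missing is the pre-specification: first-ART and switch dates are not named, and neither time on ART nor prior class is listed for adjustment.

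Finally, change of class during follow-up, freedom from the condition at baseline and evaluability at 96 weeks all matter whatever the entry route. They are not consequences of criterion 3.

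**Conclusion.** The inconsistency is in the current text and should be fixed. If criterion 3 governs, first-ART incidence is pooled with later-ART and post-switch incidence, and the class comparison is open to confounding by treatment stage and prior regimen. If the Study population and first-visit wording governs, criterion 3 is wrong as written.

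The conflict is certain; its effect on the results is not. Neither the size nor the direction of bias can be determined, because the number of recent starters and switchers is not given. A reader might infer that the INSTI comparison is biased in a particular direction; nothing in the documents supports that.

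The calculable quantity is the cost of a starter-only primary set, not the bias: the half-width rises from 3.9 points at 400 to 4.1, 4.7 or 5.5 points at an assumed 360, 280 or 200 starters.

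A reader might also look for a share of pre-treated entrants beyond which the odds-ratio statement fails. No such threshold can be given, because neither the number of factors nor the exposure split is stated and the answer moves with both.

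**What to change.** 1. Reconcile the Study design, Study population, Inclusion criteria and Data collection sections. State one baseline window and what the 24-month limit is measured from.
2. If pre-treated people remain eligible, define in the Statistical analysis section a primary set for the first objective, the hypothesis and the 96-week estimate: newly diagnosed participants whose baseline falls in the reconciled window around first ART.
3. Keep recent starters and switchers enrolled, but report them as separate strata. Make any pooled analysis secondary and have it account for time since ART start and prior class, for example by delayed entry or stratification.
4. Name first-ART and switch dates as items within the medication history already collected.
5. Restate the 96-week interval for the expected number of starters, and recheck the odds-ratio statement for the same number with the number of factors and exposure split declared.

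The cost is wording and two named dates, with no extra visits or tests. The drawback is a smaller primary set with the wider intervals shown above. If the sponsor instead limits eligibility to people within the reconciled window, items 2 and 3 largely fall away.

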#### **c. Exclusion criteria:**

1. Pregnancy
2. Refusal to consent

## **Data collection and investigations**

- a. Eligible subjects will attend Infectious Diseases clinic at the Prince of Wales Hospital for assessment.

The first study visit will be scheduled before or within four weeks of initiation of ART. Annual visits will be scheduled thereafter for 5 years. During each study visit, demographic and clinical data will be collected. Physical examination will be performed. Blood and urine tests will be done at fasting state. Imaging, including ultrasonography of carotid arteries, DEXA scan and fibroscan, will be performed. Stool samples will be collected for microbiota study.

- b. Clinical data

A structured standardized research tool will be used to collect demographic and clinical data:

1. Age, gender, smoking status, alcohol consumption, exercise
2. Co-morbid illnesses, including history or new diagnoses of hepatitis B and C, diabetes, dyslipidemia, hypertension, metabolic syndrome, and cardiovascular diseases, as well as all comorbidities included in the Charlson comorbidity score
3. Date of HIV diagnosis, latest CD4 counts, latest HIV viral load
4. Medication history, including anti-retroviral drugs and other medications

- c. Physical examination and anthropometric measurements

1. Body weight and height, and body mass index
2. Hip and waist circumferences
3. Blood pressure
4. For subjects aged  $\geq 50$  years old, assessment of frailty, including hand grip strength, balance tests, 6-metre walking speed, will be performed
5. Neurocognitive assessment
  - i. International HIV dementia scale  
<https://www.hiv.uw.edu/page/mental-health-screening/ihds>
  - ii. Montreal Cognitive Assessment
  - iii. Symbol digit modality test (SDMT)
  - iv. Action fluency: ask the patient to say as many things that people do in 1 minute
  - v. Cogstate platform neurocognitive tests
  - vi. DASS 21 for screening of mood
  - vii. Lawton Instrumental Activities of Daily Living
6. Quality of life assessment
  - i. EQ-5D-5L questionnaire
7. Lung function test
  - i. FEV1 and FVC will be performed in smokers.

- d. Blood tests:

The following blood tests will be performed after an 8-hour fast:

1. Glucose, insulin, HbA1c
2. Total cholesterol, LDL cholesterol, HDL cholesterol, triglyceride, apolipoprotein A and apolipoprotein E
3. Complete blood count, creatinine, urate, calcium, phosphate, urea, ferritin
4. Testosterone, estradiol, luteinizing hormone, follicle-stimulating hormone, free thyroxine, thyrotropin, growth hormone, cortisol
5. 25(OH) vitamin D, parathyroid hormone, calcium, alkaline phosphatase
6. Alanine aminotransferase (ALT), aspartate aminotransferase (AST), platelet count,

- bilirubin, albumin
- 7. Adiponectin, leptin
- 8. Quantitative immunoglobulins, serum paraproteins
- 9. sCD14, hsCRP, IL-6, D-dimer, sVCAM-1, sICAM, TNF- $\alpha$
- 10. HBsAg, anti-HBc, anti-HCV antibody
- 11. Cytokeratin-18 fragments using M30-Apoptosense ELISA kit (PEVIVA, Bromma, Sweden) as a marker for steatohepatitis
- e. Spot urine tests for:
  - 1. Phosphate, urate, creatinine
  - 2. Retinol-binding protein (RBP),  $\beta$ 2 microglobulin
  - 3. Protein and albumin
- f. Ultrasonography of carotid arteries
  - 1. Carotid IMT (cIMT) will be measured to provide estimates on atherosclerosis extent and progression. B-mode ultrasound examinations will be performed with Vivid E9 (GE Healthcare, Milwaukee, WI, USA) with a 11 MHz scanning frequency linear transducer. All scans will be performed by an experienced physician after a predetermined, standardized scanning protocol for the posterior wall of right and left carotid arteries using images of the far wall of the distal 10mm of the common carotid arteries. The reported cIMT value represents the mean of measurements at both left and right carotid arteries. A carotid plaque will be considered to be present when cIMT was >1.2 mm at any site.
- g. Dual energy absorptiometry (DEXA) scan:
  - 1. Site-specific bone DEXA will be performed using a Hologic QDR 4500A fan beam densitometer (Hologic, Inc., Bedford, MA) to measure hip and lumbar spine (from L1 to L4) bone mineral density (BMD) and lumbar spine trabecular bone score.
  - 2. Whole body DEXA will be performed to measure total body fat, lean body mass, and regional fat in arms, legs, and trunk (in grams). In measuring trunk fat, a line of delineation will be drawn between the head of the humerus and the glenoid fossa of the scapula to separate the upper limb from the trunk, and the leg consists of the parts of the body between the inferior border of the ischial tuberosity to the most distal tip of the toes.
- h. Fibroscan
  - 1. Liver stiffness measurement by transient elastography will be performed. Ten successful acquisitions will be performed on each subject. The median value represents the liver elastic modulus. Liver stiffness will be expressed in kiloPascal (kPa). Liver stiffness measurements will be considered valid only if 10 successful acquisitions are obtained, and the interquartile range (IQR) to median ratio of the 10 acquisitions is <0.3. Only valid liver stiffness measurements were included in the analyses involving liver stiffness.
  - 2. Controlled attenuation parameter (CAP) will be used to measure liver ultrasonic attenuation, for determination of hepatic steatosis. CAP will be computed only when the associated liver stiffness measurement is valid and using the same signals as the one used to measure liver stiffness. The final CAP value is the median of individual CAP values and will be expressed in dB/m.
- i. Automated retinal image analysis
  - 1. Digital fundus photographs will be acquired by a trained technician using a Canon CR2 AF non-mydriatic retinal camera of both eyes (Canon). Retinal vessel

measurements will be made. ARIA-stroke risk score will be calculated.

- j. Risk prediction
  - 1. Cardiovascular
    - i. 10-year risk of developing atherosclerotic cardiovascular disease will be calculated based on the Pooled Cohort ASCVD Risk Equations.
    - ii. Cardiovascular disease risk will be calculated using the DAD cohort risk prediction equation  
<http://www.hivpv.org/Home/Tools/tabid/91/ctl/ExamView/mid/500/eid/0/ld/0/Default.aspx>
  - 2. Renal disease
    - i. Risk of developing chronic kidney disease will be calculated based on the following risk scores:
    - ii. DAD risk prediction <https://www.chip.dk/Tools-Standards/Clinical-risk-scores>
    - iii. UCSF risk prediction <http://hivinsite.ucsf.edu/InSite?page=md-calculator>
  - 3. Osteoporosis/fracture
    - i. 10-year risk of fracture will be calculated using WHO Fracture Risk Assessment Tool (FRAX) score: <http://www.shef.ac.uk/FRAX/>
  - 4. Cognitive impairment
    - i. HIV international dementia scale  $\leq 10$
  - 5. Mood
    - i. Depression score  $>9$ , anxiety score  $>7$ , or stress score  $>14$  according to DASS 21 assessment

